# 4.4.4 Other biological samples

Other biological samples include biological samples obtained for hematology, urinalysis, fecal analysis, blood biochemistry, coagulation function, pregnancy-related tests, serum etiological examinations and other examinations. The collection, preservation, transportation (if applicable) and testing of these samples should follow the corresponding national regulations as well as the SOPs and manuals of the responsible facilities (including the laboratory of each study site).

# 4.5 Interim analysis

No interim analysis will be performed in this study.

# 4.6 Early Closure of the Study Site/Study Suspension/Early Termination of the Study

Reasons of early closure of the study site/study suspension/early termination of the study include but are not limited to:

- The study site has serious non-compliance issues or non-compliance issues that have not been corrected after dissuasion, such as non-compliance with the protocol or the relevant regulations or guidelines for trials.
- Any new drug toxicity is discovered, or the subject experiences unexpected severe impairment (including nonclinical and clinical manifestations).
- Enrollment and follow-up of subjects has been completed.
- The protocol is not followed.
- The drug study plan (e.g., if the sponsor considers continuation of this study is inappropriate for medical, ethical or commercial reason) is changed.
- The enrollment is too slow.
- The quality of clinical data is poor.

The Ethics Committee, the investigators, and the sponsor have the right to close the study site early, suspend or prematurely terminate part of the clinical trial or the entire clinical trial:

- If the Ethics Committee makes the above decision, the investigator should immediately report to the clinical trial institution and the sponsor and provide detailed written explanation.
- If the investigator makes the above decision without consultation with the sponsor, the

investigator should immediately report it to the clinical trial institution, the sponsor and Ethics Committee and provide detailed written explanation.

• If the sponsor makes the above decision, the sponsor should notify all relevant investigators, clinical trial institutions, and drug regulatory authorities; the investigator should immediately report to the clinical trial institution and the Ethics Committee and provide detailed written explanation.

All study materials (except documents that must be retained at the study site) must be returned to the sponsor upon early closure of the study site or early termination of the study. The investigator must store relevant documents until notification of destruction from the sponsor.

#### 4.7 Definition of Study Data Collection Cut-off

The cut-off time for data collection of this Phase I study is 8 weeks after the last subject starts the study treatment, unless the entire study is prematurely terminated (see Section 4.6). At the time of study data collection cutoff, if a subject can tolerate the study drug and remains CR/PR/SD and is willing to continue the study drug treatment, the investigator believes that the subject will still clinically benefit from the continued treatment and the investigator confirms that there is no problem in drug supply after discussion with the sponsor, the subject can continue the study drug treatment (i.e., compassionate use), until he/she meets the criteria for study treatment discontinuation or there is a drug supply problem (whichever occurs first). During the compassionate use, drug-related AEs and SAEs will be recorded according to the relevant national regulations, and the SAEs will be reported to the sponsor/CRO safety department. Routine safety monitoring should be continued as needed. The investigator will select and schedule test items at his/her own discretion and should preserve relevant documents in the source files. The sponsor will not routinely collect relative results of these tests. Data collected during compassionate use will not be included in statistical analysis of the study.

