# (8) Efficacy analyses

- **ORR:** The proportion of patients with a best overall response of CR and PR as assessed per RECIST v1.1 in all patients.
- **DCR:** The proportion of patients with a best overall response of CR, PR and SD (duration of SD ≥12 weeks) as assessed per RECIST v1.1 in all patients.
- **DOR:** The duration from the firstly documented CR or PR to the date of confirmed objective tumor progression (based on RECIST v1.1) or death for the subjects with a best overall response of CR or PR. For the patients who have no objective tumor progression or death at the end of trial, the date of the last objective tumor assessment will be taken as the censored date of DOR.
- **PFS:** The duration from the first dose of study drug to objective tumor progression (based on RECIST v1.1) or death. For the patients who have no objective tumor progression or death at the end of trial, the date of the last objective tumor assessment will be taken as the censored date of PFS.
- **OS:** The duration from the first dose of study drug to death. For patients who are alive at the end of trial, their last date known to be alive will be used as the censored date of OS.

Point estimates of ORR and DCR and their two-sided 95%CI will be calculated. The two-sided 95% CI of ORR and DCR are calculated based on the Clopper-Pearson method. Meanwhile, the number and percentage of subjects with CR, PR, SD and disease progression will be presented.

For DOR (for subjects experiencing CR and/or PR only), PFS and OS, Kaplan-Meier method will be adopted to calculate the median, lower quartile, upper quartile and two-sided 95% CI, and survival curves will be drawn.

For ORR, the estimated objective is shown in the table below.

Estimated objective:					
Population:	FGF19 or FGFR4 positive advanced primary HCC or other				
	advanced solid tumors				
Treatment:	See Section 6 of the main body for details				
Endpoint:	ORR				
Intercurrent events and	• Discontinuation of study treatment or initiation of new				
handling strategies:	anticancer therapy prior to CR or PR will be handled				
	according to the while-on-treatment strategy.				

Summary at the	ORR and corresponding two-sided 95%CI (estimated by					
population level:	Clopper-Pearson method) will be calculated					
for DOR, the estimated ob	jective is shown in the table below.					
Estimated objective:						
Population:	FGF19 or FGFR4 positive advanced primary HCC or other advanced solid tumors					

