#### Note:

a. Tumor assessments will be performed on subjects whose tumor has not progressed in the last assessment until the subject is lost to follow-up, the subject dies, the subject starts new anti-tumor therapy, the subject requests to withdraw from the trial and refuses to continue follow-up, the research data collection had reached the cutoff date, the study site is early closed, the study is early terminated, or the study ends (whichever occurs first).

b. During the follow-up period after the end of the study treatment, all subjects will be followed up for the survival period and the tumor treatment status will be recorded until the subject is lost to follow-up, the subject dies, the subject requests to withdraw from the trial and refuses to continue follow-up, the research data collection had reached the cutoff date, the study site is early closed, the study is early terminated, or the study ends (whichever occurs first).

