#### 7.2 Expansion Trial

#### **Primary endpoints:**

• Efficacy of BB102 tablets (fasted): ORR, DCR, DOR, PFS and OS.

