# 10.2 Statistical Analysis Set

- ① Screening set: All subjects who signed the ICF. The screening set is used to analyze the number of subjects screened, number of subjects enrolled and number of screening failures.
- ② Safety set (SS): All subjects who are enrolled and have taken the study drug. SS is used for the description of demographic data, description of baseline characteristics, safety analysis and efficacy analysis.
- ③ **DLT analysis set (DS):** All subjects who are enrolled and have taken the study drug, but excluding subjects who receive study drug at a dose less than 75% of the scheduled dose for reasons other than toxicities attributable to study drug during the DLT observation period. DS is used for the analysis and summary of DLT.
- **PK analysis set (PKS):** All subjects who are enrolled, have taken the study drug, have at least one PK data for statistical analysis and have no any protocol deviation (e.g., missed dosing of BB102 tablets) that significantly affects the PK parameters [e.g., area under the concentration-time curve (AUC), Cmax, etc.] during the treatment cycle or dosing period containing blood sampling time point. Whether a subject is included into PKS will be determined case by case on the data review meeting. PKS is used for the analysis of PK parameters.
- (5) **Biomarker analysis set (BS):** All subjects who have at least one biological sample for biomarker analysis in the SS. BS is used for the analysis of relationship between biomarker and efficacy.

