# 10.4.8 Efficacy analyses

- **ORR:** The proportion of patients with a best overall response of CR and PR as assessed per RECIST v1.1 in all patients.
- **DCR:** The proportion of patients with a best overall response of CR, PR and SD (duration ≥12 weeks) as assessed per RECIST v1.1 in all patients.
- **DOR:** The duration from the firstly documented CR or PR to the date of confirmed objective tumor progression (based on RECIST v1.1) or death for the subjects with a best overall response of CR or PR. For the patients who have no objective tumor progression or death at the end of trial, the date of the last objective tumor assessment will be taken as the censored date of DOR.
- **PFS:** The duration from the first dose of study drug to objective tumor progression (based on RECIST v1.1) or death. For the patients who have no objective tumor progression or death at the end of trial, the date of the last objective tumor assessment will be taken as the censored date of PFS.
- **OS:** The duration from the first dose of study drug to death. For patients who are alive at the end of trial, their last date known to be alive will be used as the censored date of OS.

Point estimates of ORR and DCR and their two-sided 95%CI will be calculated. The two-sided 95% CI of ORR and DCR are calculated based on the Clopper-Pearson method. Meanwhile, the number and percentage of subjects with CR, PR, SD and disease progression will be presented.

For DOR (for subjects experiencing CR and/or PR only), PFS and OS, Kaplan-Meier method will be adopted to calculate the median, lower quartile, upper quartile and two-sided 95% CI, and survival curves will be drawn.

For ORR, the estimated objective is shown in the table below.

Estimated objective:		
Population:	FGF19 or FGFR4 positive advanced primary HCC or other advanced solid	
	tumors	
Treatment:	See Section 6 for details	
Endpoint:	ORR	
Intercurrent events and handling strategies:	Discontinuation of study treatment or initiation of new anticancer therapy prior to CR or PR will be handled according to the while-on-treatment strategy.	
Summary at the population level:	ORR and corresponding two-sided 95%CI (estimated by Clopper-Pearson method) will be calculated	

For DOR, the estimated objective is shown in the table below.

Estimated objective:		
Population:	FGF19 or FGFR4 positive advanced primary HCC or other advanced solid	
	tumors	
Treatment:	See Section 6 for details	
Endpoint:	DOR	

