## (3) Duration of stable disease

Stable disease is measured from the start of the treatment (in randomised trials, from date of randomisation) until the criteria for progression are met, taking as reference the smallest sum on study (if the baseline sum is the smallest, this is the reference for calculation of PD).

The clinical relevance of the duration of stable disease varies in different studies and diseases. If the proportion of patients achieving stable disease for a minimum period of time is an endpoint of importance in a particular trial, the protocol should specify the minimal time interval required between two measurements for determination of stable disease.

Note: The duration of response and stable disease as well as the progression-free survival are influenced by the frequency of follow-up after baseline evaluation. It is not in the scope of RECIST to define a standard follow-up frequency. The frequency should take into account many parameters including disease types and stages, treatment periodicity and standard practice. However, these limitations of the precision of the measured endpoint should be taken into account if comparisons between trials are to be made.

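### Data collection closes 8 weeks after the last start, but DCR, a primary expansion endpoint, needs 12 weeks of stable disease: if expansion subjects start last, their DCR is biased downward

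*Protocol*

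**What the plan says.** - **Cut-off.** Section 4.7, repeated in the synopsis under Study Procedures: "The cut-off time for data collection of this Phase I study is 8 weeks after the last subject starts the study treatment". It is a single date for escalation and expansion together.
- **Data after cut-off.** Subjects doing well may stay on drug as compassionate use, but "Data collected during compassionate use will not be included in statistical analysis of the study" (Section 4.7). The notes to Section 4.3.5 end tumour and survival follow-up once "the research data collection had reached the cutoff date".
- **Endpoint.** Section 7.2 lists the expansion trial's primary endpoints as "Efficacy of BB102 tablets (fasted): ORR, DCR, DOR, PFS and OS".
- **Definition.** Section 10.4.8 defines DCR as the proportion with a best overall response of "CR, PR and SD (duration ≥12 weeks) as assessed per RECIST v1.1 in all patients"; the synopsis gives the same rule. DCR is reported as a proportion with a Clopper-Pearson interval.
- **Denominator.** Section 10.2: "SS is used for the description of demographic data, description of baseline characteristics, safety analysis and efficacy analysis", where SS is every enrolled subject who took study drug.
- **SD clock.** Appendix I: "Stable disease is measured from the start of the treatment".
- **Scans.** Section 4.3 schedules tumour assessment at the end of Cycle 1 (±1 day) and then every two cycles (±7 days). CR or PR is to be confirmed 4 to 8 weeks after it is first seen. Cycles last 21 days (Section 5.2), and the single-dose phase applies to escalation only (Section 4.3.2).

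**The concern.** The last subject to start has 8 weeks of possible follow-up, and the endpoint asks for 12. A late starter with stable disease at cut-off is neither a DCR success nor removed from the denominator. Appendix I points the same way: a subject with SD short of the minimum duration and no later scan is inevaluable, yet all patients must be accounted for. Because DCR is a simple proportion, no censoring absorbs the shortfall, unlike PFS, DOR and OS, which are censored and are not part of this point.

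The error runs in one direction and reflects enrolment timing, not the drug. The protocol does not fix who starts last. Expansion may begin before escalation ends (Section 4.1.2), and the fed group may run after the fasted groups (Section 4.1.1.3). But expansion doses must first pass the DLT criterion in escalation, so expansion may well finish last. Section 10.3 makes the analysis descriptive with no test, so the harm is to a primary estimate and not to an error rate.

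**Working it through.** **What the plan itself gives.** It states no accrual rate and no expected DCR. The only figure to reproduce is enrolment (Section 10.1). Escalation is 1 + 5×3 + 3 (fed) = 19 to 7×6 = 42, and expansion is 12 to 3×12 = 36. The totals are 31 and 78, as stated.

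**Scan times in expansion.** The ends of Cycles 1, 3 and 5 are days 21, 63 and 105, which is weeks 3, 9 and 15. The ±7-day windows are weeks 8–10 and 14–16. The first scheduled scan at or after week 12 is the week-15 scan.

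**Who is affected.** A subject starting x weeks before the last subject has 8 + x weeks of follow-up at cut-off.

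- Reaching 12 weeks requires 8 + x ≥ 12, so x ≥ 4.
- Having the week-15 scan requires 8 + x ≥ 15, so x ≥ 7 (x ≥ 6 if it is taken at week 14).
- Confirming a response first seen at week 9 requires week 13, so x ≥ 5 (x ≥ 4 if first seen at week 8). A response seen at the end of Cycle 1 can still be confirmed, so ORR is affected less.

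**Assumed SD rate.** Two similar drugs in the protocol give a range; neither is this drug or this mixed population.

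- H3B-6527 (Section 1.3): clinical benefit 45.8% − response 16.7% = 29.1%, with SD beyond 17 weeks.
- FGF401 phase I monotherapy (Section 1.7): DCR 45.9% − ORR 5.4% = 40.5%, with no minimum SD duration stated.

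**Loss in DCR.** Assume uniform expansion accrual over T weeks with an expansion subject last overall. Loss = (4/T or 7/T) × SD rate.

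| T (weeks) | 4/T | Loss, 4-week rule (points) | 7/T | Loss, 7-week rule (points) |
|---|---|---|---|---|
| 13 | 0.308 | 9.0 to 12.5 | 0.538 | 15.7 to 21.8 |
| 26 | 0.154 | 4.5 to 6.2 | 0.269 | 7.8 to 10.9 |
| 52 | 0.077 | 2.2 to 3.1 | 0.135 | 3.9 to 5.5 |

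At 29.1% under the 7-week rule, a group of 12 loses 12 × 0.078 = 0.9 patients (26 weeks) or 12 × 0.039 = 0.5 (52 weeks).

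**Small-group check.** Take n = 12 with the first start at week 0, the last at week T and the other ten uniform between. The share with under 15 weeks of follow-up is (1 + 10 × 7/T)/12, which is 30.8% at T = 26 and 19.6% at T = 52. The large-sample shares of 26.9% and 13.5% therefore do not overstate it.

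**Floor.** In the group of 12 that contains the last subject, at least 1/12 = 8.3% is affected at any accrual pace. The expected loss is at least 29.1/12 = 2.4 to 40.5/12 = 3.4 points. Pooled over 36 expansion subjects it is 29.1/36 = 0.8 to 40.5/36 = 1.1 points.

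**The case against.** The mismatch itself is not in dispute; the case against concerns size and importance.

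- **The effect is conditional.** Only starters in roughly the last 4 to 7 weeks are affected, and the permitted enrolment order could make the loss zero. This stands, and is why the conclusion is conditional.
- **The 7-week rule is an inference.** The protocol does not say how SD without progression is timed at cut-off, and an SAP could settle that. Only the 4-week rule follows from the text alone. With the scan at week 14, the 26-week loss is 6/26 × 29.1 = 6.7 to 6/26 × 40.5 = 9.3 points. This stands: the 4-week figures are the firmer ones.
- **The 40.5% rate probably includes SD shorter than 12 weeks.** This is fair, so the lower end of each range is better supported.
- **Accrual in 13 weeks is fast.** Section 4.9 gives about 24 months. Less 8 weeks that is 96 weeks, so 31 to 78 subjects is 0.32 to 0.81 per week, and 12 subjects take about 15 to 37 weeks. The 26-week row is the more natural one, although expansion could enrol faster than the study average.
- **The practical consequence is small.** There is no test and no DCR threshold, and a Clopper-Pearson interval for 5/12 runs from 15% to 72%. A loss of under one patient sits well inside that. But a wide interval does not correct an error that always points down.

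None of this removes the fault. An SAP could add a restricted DCR, but it cannot recover scans that were never collected.

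**Conclusion.** The concern holds. The cut-off, the exclusion of later data, the 12-week SD minimum and the all-patients denominator are all fixed in the protocol, and together they understate the expansion DCR whenever expansion subjects are among the last to start. With 26-week accrual the loss is 4.5 to 6.2 points on the rule that follows directly from the text. It is 7.8 to 10.9 points if a scan at or after week 12 is required. With 52-week accrual the figures are 2.2 to 3.1 and 3.9 to 5.5. These rest on assumed uniform accrual, an expansion subject last overall, and SD rates borrowed from similar drugs. The loss is zero if a subject from another part starts 7 or more weeks after the last expansion subject. The point should be fixed, but it threatens a descriptive estimate and not a formal decision.

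**What to change.** **Main change.** In Section 4.7 and the synopsis, set the efficacy cut-off at the later of the current date and 18 weeks after the last expansion subject's first dose. Include tumour and survival data to that date for subjects continuing on drug. Eighteen weeks covers the week-15 scan (window to week 16). It also covers confirmation of a week-9 response (weeks 13–17, or 18 if the scan was a week late), but not confirmation of a response first seen at week 15.

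The cost is up to 18 − 8 = 10 more weeks of collection, with one or two scans and survival contacts for subjects still followed, and no extra patients. The cut-off wording in the notes to Section 4.3.5 would have to follow. Scheduled scans must also continue to the new date, because Section 4.7 now leaves testing after cut-off to the investigator.

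**Fallback if 8 weeks is kept.** Beside the all-treated results, report DCR among subjects first dosed at least 16 weeks before cut-off, and confirmed ORR among those first dosed at least 18 weeks before. The SAP can specify this and it needs no new data, but the denominators shrink:

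- 26-week accrual: 12 × (1 − 8/26) = 8.3 of 12 for DCR and 12 × (1 − 10/26) = 7.4 for ORR.
- 52-week accrual: 12 × (1 − 8/52) = 10.2 for DCR and 12 × (1 − 10/52) = 9.7 for ORR.

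Late escalation subjects have the same gap in DCR, a secondary endpoint there (Section 7.1), so the restricted figure could be given for them too.

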#### 4.8 Number of Study Sites

This trial is planned to be carried out at 3-6 study sites in the United States of America.

#### 4.9 Study Duration

Approximately 24 months.

# 5. Study Medication

# 5.1 Drug Name, Dosage Form and Other Basic Information

# 5.1.1 Investigational product (BB102 tablets)

Table 2 Basic information of BB102 tablets

Generic name:	BB102 Tablets	
Dosage form:	Tablet	
Active ingredients:	BB102	
Molecular formula of active ingredient:	$C_{26}H_{30}N_8O_4\cdot C_6H_8O_7$	
Appearance of active ingredients:	Off-white powder	
CAS number of active ingredient:	None	
Molecular weight of active ingredient:	1 /10 /0	
Strength:	10 mg、50 mg	
Package specification:	50 tablets/bottle	
Shelf life:	24 months tentatively	
Drug source:	Provided by the sponsor	

# 5.1.2 Control drug

No control drug is designed in this trial.

#### 5.2 Method of Administration

1. **Dose levels:** possibly 50 mg QD, 100 mg QD, 160 mg QD, 240 mg QD, 320 mg QD and 420 mg QD (for the dose escalation groups, the escalation doses may be adjusted according to the previously obtained clinical trial data of BB102 tablets, e.g., adding dose groups of 520 mg QD and 600 mg QD).

2. Administration route: Oral.

#### 3. Administration method:

For dose groups 1, 2, 3, 4, 5 and 6 in the dose escalation trial, subjects will be fasted overnight for at least 10 hours before dosing on D1 and C1D21 and take BB102 tablets with about 240

- mL of water; no drinking is allowed from 1 h pre-dose to 1 h post-dose; and no food is allowed within 2 h post-dose. Subjects will be on a normal diet.
- For dose groups 1, 2, 3, 4, 5 and 6 in the dose escalation trial, subjects will be fasted at least 2 hours before dosing on the other dosing days, and take BB102 tablets with water; no food is allowed within 1 h post-dose. Subjects will be on a normal diet.
- For dose groups A in the dose escalation trial, subjects will be fasted overnight for at least 10 hours before dosing on D1 and C1D21, start eating a low-fat meal at 30 min before dosing on D1 and C1D21 (breakfast), finish the meal within 30 min and take BB102 tablets with about 240 mL of water at 30 min from the start of meal (if the meal takes more than 30 minutes, BB102 tablets should be administered immediately after the meal); no drinking is allowed from 1 h pre-dose to 1 h post-dose; no food is allowed within 4 h post-dose. Except for the low-fat meal (breakfast) on the specified days, subjects will be on a normal diet.

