It is planned to enroll 3 subjects to other groups, and the specific dose escalation method is shown in Figure 3. For each dose group, if none of the 3 subjects experiences DLT, the trial will proceed

to the next dose group. If  $\geq 2$  out of the 3 subjects experience DLT, the dose escalation will be discontinued. If 1 of the 3 subjects experiences DLT, 3 additional subjects should be enrolled into this dose group (if none of the 3 newly enrolled subjects experiences DLT, the trial will proceed to the next dose group; If  $\geq 1$  of the 3 newly enrolled subjects experience DLT, dose escalation will be discontinued).

[figure not shown]

Figure 3 The 3+3 escalation diagram in dose escalation trial

The second and third subjects in the 3+3 escalation groups should only be enrolled after the first subject is observed for at least 5 days after dosing (enrolled on or after C1D1 of the first subject). If the previous subject experiences DLT, the sponsor and the investigator need to cautiously judge whether to enroll the next subject based on the safety data; if subsequent subjects have already been enrolled, the enrolled subjects should continue the study treatment (unless these subjects meet the criteria for study treatment discontinuation), with his/her safety data closely monitored.

SMC will decide whether to perform dose escalation or reduction and determine whether to and how to adjust the escalation doses based on the safety, tolerability and/or PK data obtained during the DLT observation period of a certain dose group. Based on the safety, tolerability, PK and efficacy data of a certain group, if the investigator believes that it is necessary to expand the number of subjects of this dose group to further observe the safety and efficacy and obtain PK data, the number of subjects of this dose group may be increased to 4-12 after reaching a consensus with the sponsor through discussion.

To ensure the safety of subjects, the washout time after single-dosing, dosing frequency, cycle setting, and time points of PK sample collection in the subsequent study as well as the design of subsequent escalation doses (e.g., adding dose groups of 520 mg QD and 600 mg QD) may be

timely adjusted based on the previously obtained safety, tolerability, PK parameters [e.g.,  $T_{1/2}$ , drug accumulation after multiple-dosing] and other previously obtained clinical trial data of BB102 tablets.

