#### **Composition of the low-fat meal:**

Total calories (kcal)	400-500	
Fat (g)	11-14	
Calories from fat (%)	25	
An example of a low-fat breakfast*	• Eight ounces milk (1 percent fat)	
	One boiled egg	
	One packet flavored instant oatmeal made with	
	water	

\*Note: 25% of calories are derived from fat. Substitutions can be made to this meal, if the content, volume, and viscosity are maintained. A registered dietician at the study site should determine the appropriate meal to be consumed, based on the fat and calorie requirements assigned to the patient for that treatment day. The start/stop time of meal consumption, and estimated % of test meal consumed (based on fat and caloric content), must be listed in the meal record eCRF for patients allocated in exploratory food effect group.

- For dose group A in the dose escalation trial, subjects will take BB102 tablets with water within 30 minutes following the meal on the other dosing days; no food is allowed within 1 h post-dose. Subjects will be on a normal diet.
- In the expansion trial, subjects will be fasted for at least 2 hours before dosing and take BB102 tablets with water; no food is allowed within 1 h post-dose. Subjects will be on a normal diet. Note: The administration method of the expansion trial may be adjusted according to the previously obtained food effect evaluation results of BB102 tablets.
- **4. Dosing frequency and cycles:** once daily in 21-day cycles (the dosing frequency and cycle setting may be adjusted according to the previously obtained clinical trial data of BB102 tablets).

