#### 10.4.7 Analysis of food effect

Data analysis will be performed by the average bioequivalence method with fasted condition as the reference, and the exposure parameters (AUC0-inf, AUC0-t and Cmax) will be log transformed using natural logarithm to calculate the geometric mean ratio of fed group to fasted group and its 90% CI. If the 90% CI of the geometric mean ratios (fed group/fasted group) of AUC0-inf (or AUC0-inf) (or AUC0-inf

 $_{\rm t}$ ) and  $C_{\rm max}$  all fall within the range of 80%-125%, it can be preliminarily concluded that food has no significant effect on the bioavailability of the drug.

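### On the PK profile days the fasted groups may eat from 2 h after dosing and the fed group only from 4 h, so the fed/fasted ratio does not isolate the pre-dose meal

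*Protocol*

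**What the plan says.** Section 5.2 (Administration method), repeated in the synopsis under Investigational Drug, gives the D1 and C1D21 rules by group.

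- Fasted groups 1-6: "subjects will be fasted overnight for at least 10 hours before dosing on D1 and C1D21", then the tablets with about 240 mL of water, "and no food is allowed within 2 h post-dose".
- Fed group A: the same overnight fast, a low-fat breakfast started 30 min before the dose, then "no drinking is allowed from 1 h pre-dose to 1 h post-dose; no food is allowed within 4 h post-dose".
- Later food is not standardised in either condition. For group A the text reads "Except for the low-fat meal (breakfast) on the specified days, subjects will be on a normal diet", and groups 1-6 are also on a normal diet.

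Section 10.4.7 uses these data: "Data analysis will be performed by the average bioequivalence method with fasted condition as the reference". It forms fed/fasted geometric mean ratios of AUC0-inf, AUC0-t and Cmax. It allows a preliminary conclusion of no significant food effect if the 90% confidence intervals "all fall within the range of 80%-125" per cent. Section 5.2 adds that the way the drug is taken in the expansion trial may be adjusted on the food-effect results.

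**The concern.** A fed/fasted contrast should differ only in the meal before the dose. Here the fasted reference may take an uncontrolled meal between the 2 h and 4 h samples while the fed group may not. If drug is still being absorbed then, the reference is partly fed.

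On all other dosing days both conditions share a 1 h post-dose interval. The conditions therefore differ after the dose only on the two days when they most need to match.

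The effect of food on PK is a secondary objective (section 2.1), and its result can feed into how expansion subjects take the drug. Confounding built into the dosing conditions cannot be removed in the analysis.

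**Working it through.** **1. The rules side by side (section 5.2)**

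| | Groups 1-6 (fasted) | Group A (fed) |
|---|---|---|
| No food after dose, D1 and C1D21 | 2 h | 4 h |
| No food after dose, other days | 1 h | 1 h |
| PK samples, first 10 h of profile days (section 4.4.1) | 1, 2, 4, 6, 8, 10 h | same |

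Nothing elsewhere in the protocol aligns or explains the 2 h and the 4 h.

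**2. What the documents say about absorption and food**

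- Humans: no data (section 1.6), hence no Tmax or absorption rate.
- Rat timing (section 1.5.2): most tissues peaked at 30 min and a few at 2 h, which points to fast absorption.
- Rat exposure: from 30 to 270 mg/kg, AUC/Cmax rose from 27209/5927 = 4.6 h to 160093/10253 = 15.6 h in males, and from 36269/8733 = 4.2 h to 297985/15700 = 19.0 h in females, while half-life stayed between 4.5 and 6.8 h. This is consistent with slower absorption at high doses. However, 30 mg/kg already converts to 30/36.88 × 6.60 × 60 = 322 mg, so the higher rat doses lie above the planned 420 mg.
- Rat food effect: fasted/fed AUC was 1.21 in males and 1.02 in females, i.e. fed/fasted 1/1.21 = 0.83 and 1/1.02 = 0.98. The protocol reads this as no significant effect.

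**3. Illustration of size (assumptions throughout)**

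The protocol states no expected ratio, SD or power for this comparison, so there is no figure of its own to reproduce.

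Assume first-order absorption at rate ka. Food multiplies the availability of drug absorbed in the fed state by R, the later meal acts like the test meal, and subjects eat as soon as allowed. With u = exp(-ka × t) unabsorbed when the fasted group eats at time t:

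observed AUC ratio = R / (1 + (R - 1) × u)

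Example, R = 1.5 and ka = 0.5 per h:

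- t = 2 h: u = exp(-1) = 0.37, ratio = 1.5/1.184 = 1.27.
- t = 4 h: u = exp(-2) = 0.135, ratio = 1.5/1.068 = 1.40.

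Cmax comes from a one-compartment model with an assumed 6 h half-life (dog values are 6.30-7.26 h). The common 4 h interval serves only as an example.

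| ka (per h) | Unabsorbed at 2 h | AUC ratio, 2 h rule | AUC ratio, common 4 h | Cmax ratio, 2 h rule | Cmax ratio, common 4 h |
|---|---|---|---|---|---|
| 2 | 0.02 | 1.49 | 1.50 | 1.50 | 1.50 |
| 1 | 0.14 | 1.40 | 1.49 | 1.44 | 1.50 |
| 0.5 | 0.37 | 1.27 | 1.40 | 1.29 | 1.48 |
| 0.25 | 0.61 | 1.15 | 1.27 | 1.16 | 1.32 |

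For R = 0.7 the AUC ratios, in the same ka order, are 0.70, 0.73, 0.79 and 0.86 under the 2 h rule, against 0.70, 0.70, 0.73 and 0.79.

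**4. Direction**

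Let the low-fat meal have no effect (R = 1) and the later normal meal multiply availability by 1.5 to 2.0. The AUC ratio is then 0.83 to 0.99 under the 2 h rule and 1.00 under a common interval. The bias is away from 1.

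**5. Could the 80%-125% rule then be met falsely?**

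The rule concerns the confidence interval. For two parallel groups of n, its half-width on the log scale is t × SD × sqrt(2/n).

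- n = 3 (4 df, t = 2.132): 2.132 × 0.816 × SD = 1.74 SD.
- n = 12 (22 df, t = 1.717): 1.717 × 0.408 × SD = 0.70 SD.

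The upper limit fits if SD is at most ln(1.25/estimate) divided by that factor.

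| AUC estimate | ln(1.25/estimate) | Largest SD, n = 3 | Largest SD, n = 12 |
|---|---|---|---|
| 1.18 (ka 0.3) | 0.058 | 0.033 | 0.08 |
| 1.15 (ka 0.25) | 0.083 | 0.048 | 0.12 |
| 1.05 (ka 0.25, later meal factor 2.0; common interval 1.23) | 0.174 | 0.10 | 0.25 |

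The protocol gives no between-subject SD.

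**The case against.** The opposing case has substance. The only timing data, in rats, suggest fast absorption, and at ka = 2 the unequal intervals cost nothing. The rat food-effect ratios are smaller than the assumed 1.50 and point the other way. The 2 h limit is a minimum wait, not a scheduled meal, so the illustration takes the earliest permitted time. With slow absorption a common interval would not recover 1.50 either; only the difference between the two columns belongs to the unequal rule. The protocol calls the evaluation preliminary. All of this stands and limits the size and certainty of the effect. It does not explain why the intervals differ, and rat data cannot establish that human absorption is complete by 2 h.

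A reader might infer that the ratio is necessarily pulled toward 1, or that a false finding of no food effect becomes likely. The documents support neither. The first needs absorption still under way at 2 h and a later meal acting like the test meal. The second runs into the group size: "It is planned to enroll 3 subjects to other groups". With three per group, the interval fits 80%-125% only at very small SDs. It is less remote if groups are enlarged toward the permitted 12 and the later meal is the stronger one.

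A reader might also see a contradiction between the no-drinking window and the example breakfast, which includes "Eight ounces milk (1 percent fat"). That is too literal. The same instruction orders 240 mL of dosing water and a prescribed meal inside the window, so the evident meaning is no other drinking.

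**Conclusion.** The 2 h against 4 h difference is certain from the text and unexplained. It falls on the two full-profile days, so the food-effect ratios compare conditions that differ in more than the pre-dose meal.

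The consequence is conditional. If absorption continues past 2 h, the comparison is confounded and a real effect may be diluted toward 1. In the illustration the shift in AUC ratio runs from 0.01 (1.49 against 1.50) to 0.13 (1.27 against 1.40), and at the slowest rate shown the point estimate moves from 1.27 to 1.15, across the 1.25 limit. These values rest on assumed absorption rates, an assumed food effect and a meal at the earliest allowed time. The sign can reverse. This is a modest design flaw that is easily removed, not evidence that the food-effect conclusion will be wrong.

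**What to change.** Reconcile the group 1-6 and group A instructions in section 5.2 and the synopsis so that both conditions have one identical post-dose no-food interval on D1 and C1D21. This should cover all of groups 1-6, or at least the fasted group at the dose given to group A. The sponsor should choose the interval.

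The cost is protocol wording. Depending on the interval chosen, one group may wait longer to eat on two days. The change should precede the first profile day of any group that may serve as the reference.

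Optionally, state that the dosing water and the liquids in the test meal are exempt from the no-drinking window. This is a clarification only.
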